#### 4. STUDY DESIGN

# 4.1. General Description

This is a Phase 1, open-label, dose-escalation, 2-part study in adult patients with advanced malignancies known to overexpress the WT1 protein. The study will primarily evaluate DLT and define the MTD of WT2725 Dosing Emulsion during the DLT Evaluation Period, which extends from the day of the first dose of study drug to just prior to the fifth dose (Days 1 - 29). In addition, antitumor activity and biomarkers indicative of immune response will be evaluated from the first dose until discontinuation of the patient from the study. An end of study assessment will take place within 28 days after the last dose of study drug and prior to the start of alternate antineoplastic therapy.

The initial patients in each dose escalation cohort will be enrolled at least one week apart to evaluate initial safety from the first 2 patients, then a "rolling-six" design will be employed that allows accrual of 2 to 6 patients concurrently in each dose escalation cohort.

In Part 1 of the study, the 0.3 mg cohort will be conducted first. After safety and tolerability have been established for the first cohort, enrollment of subsequent patients will be conducted sequentially in subsequent cohorts and continue until the MTD or all planned cohorts are attained. Enrollment of each cohort may include patients with any of the eligible tumor types (see below). Enrollment of the highest tolerable dose cohort (MTD or highest planned cohort) will continue until there are at least 6 patients total in the study with each tumor type that are evaluable for DLT, biomarkers, and response. This dose is considered the recommended phase 2 dose (RP2D). Enrollment of up to 3 RP2D cohorts of 10 patients each of a specific tumor type may take place at this dose in order to further characterize the safety and efficacy of WT2725 Dosing Emulsion at this

dose in these subsets of patients. Additional dose escalation cohorts after the initial expansion cohorts may be enrolled if a MTD has not been determined and significant signs of toxicity have not been observed in the expansion cohorts.

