#### Part 2:

• 18.0 and 27.0 mg WT2725 Dosing Emulsion

All study drug will be administered by sc injection (at 2 anatomical sites) once every 7 days for 8 weeks, then once every 14 days for 10 weeks, and then once every 28 days until discontinuation.

[figure not shown]
Approximately 60 to 80 patients total in Parts 1 and 2 including replacements will be dosed in this clinical trial. Part 1: 4-8 clinical sites in the United States (US) and Part 2: an additional 2 sites in US may be utilized to enroll patients.

The following list contains the definitions of some important terminology in this study:

- DLT: defined as any Grade 3 or greater AE that occurs after the administration of study drug during the DLT Evaluation Period that is not related to underlying disease, intercurrent illness, or concomitant medications. (Changes in hematology parameters need to have been confirmed on repeat assessment and constitute at least a 2 grade shift. Grade 3 AEs of nausea, vomiting, and fatigue that are common and manageable in cancer patients will not be considered DLT if they can be ameliorated to < Grade 3 with standard supportive care management). AEs will be graded according to the Common Terminology Criteria for Adverse Events (CTCAE) V.4.0 (National Cancer Institute [NCI]-2009).
- DLT Evaluation Period: extends from the day of the first dose of study drug to just prior to the fifth dose (Days 1-29). No more than 4 doses of study drug will be administered during the DLT Evaluation Period.
- An evaluable patient: defined as a patient who has a DLT or a patient who completes the DLT Evaluation Period without the occurrence of a DLT.
- MTD: defined as the dose at which no more than 1 of 6 patients experiences a DLT when 2 or more of 2 to 6 patients experiences a DLT at the next higher dose cohort.

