# 8. STATISTICAL ANALYSIS

In this section and all after, when tables are presented by posttreatment visits, the last visit will be the visit at the end of study. When applicable, visits after the start of the maintenance phase and unscheduled visits will be included in a summary of maximum and minimum values observed for each patient's posttreatment visits, i.e., the minimum and maximum values are based on all the post treatment visits.

In general descriptive statistics for continuous variables will be summarized by the mean, standard deviation, 25th percentile, median (50th percentile), 75th percentile, minimum and maximum values. When continuous variables are displayed for less than 3 patients, only the number of observations will be presented. Categorical variables will be summarized using counts and percentages.

All raw data will be presented to the original number of decimal places. The means and medians will be presented to 1 more decimal place than the raw data. The standard deviations will be presented to 2 more decimal places than the raw data.

Baseline will generally be defined as data obtained as the last non-missing value prior to the first dose of study drug, i.e., including the pre-dose assessment on Day 1, assessments during screening and other assessments prior to the first dose of study drug.

AE tables and laboratory tables will be presented by visits and by tumor group. Tumor groups are defined as groups of overall, solid tumor, and AML patients.

Unless otherwise stated, summaries will be produced by dose cohort, which is defined as the intended and starting dose to which the patient was enrolled.

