## 8.3. Analysis Populations

There are 3 planned analysis populations.

- Safety population: includes all enrolled patients who receive at least 1 dose of study drug and will be used for the analysis of all safety and efficacy data except as noted below
- DLT population: includes all patients in the Safety population who experience a DLT within the DLT evaluation period or completed the DLT evaluation without experiencing a DLT and will be used for analysis of DLT.
- Efficacy population: include all patients in the Safety population who are evaluable for response (for each irRC, IWG, CA-125 and WT1 by RT-PCR)
  - o Population for irRC response: including all the patients in the Safety population who are not AML patients and whose lesions are measureable and have at least one posttreatment assessment. (Note that any posttreatment irRC assessment is based on the baseline assessment)
  - O Population for modified IWG response: includes all the AML patients in the Safety population who have >5% marrow blasts or >50 copy/μ g RNA of quantitative RT-PCR for WT1 transcript before the first date/time of study drug and who have at least one posttreatment assessment.
  - o Population for CA-125 tumor marker: including all ovarian cancer patients in the Safety population who have a baseline CA-125 assessment and at least one assessment posttreatment.
  - Population for WT1 by RT-PCR tumor marker: includes AML patients in the Safety population who have a baseline assessment and at least one assessment posttreatment.
- Population for CTL: including all patients in the Safety population who has a baseline assessment of percentages of WT1-positive cells among CD8-positive cells and at least one post-baseline assessment

Additional populations for analyses of other tumor markers identified may be defined in a similar manner.

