## 8.6.3. Exploratory Analyses

The Population for Biomarkers includes all patients in the Safety population who have the Day 29 biomarker assessment completed. All other exploratory analyses will use all patients in the Safety population of patients with the endpoint of interest measured at baseline and at least once posttreatment.

Biomarker sample collection will be conducted as indicated on the Schedules of Assessment (Table 1 and 2). Tables may summarize the statistics at the screening assessment, at each posttreatment visit, and at the end of study.

A table will summarize the Spearman rank correlation and 95% CI between the level of expression of WT1 protein and the degree of the immune response by dose cohort at each visit as measured by CTL induction. Additionally, the correlation at each visit may be presented graphically.

Scatter plots of maximum (mean, median) post-baseline values of immune response measured by CTL induction versus maximum (mean, median) post-baseline values of CA-125 will be presented. Additionally, scatter plots of maximum (mean, median) post-baseline values of immune response measured by CTL induction versus maximum (mean, median post-baseline values of WT1 by RT-PCR will be presented.

A listings of level of expression of WT1 protein will be provided.

If additional reports are provided by the biomarker vendor(s) then additional analyses may be performed and the vendor's report will be an appendix to the clinical study report.

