#### 8.6.3.1. CTL Evaluation

A patient is considered a CTL responder if s/he has:

• Two or more post-baseline visits (no need to be consecutive) with >=2-fold increase from baseline, if the baseline is not 0,

Or

 Only one post-baseline visit with >=2-fold increase from baseline when the total number of post-baseline visits is <=4, if the baseline value is not 0,

 Or

• At least one post-baseline value > 0, if a patient has baseline of 0

A table will present the number and percentage of patients for their CTL response. Additionally, geometric mean, geometric SD, the mean, standard error (se), SD, median, 25 and 75 percentile of baseline assessments and the corresponding same descriptive statistics for both mean of post-baseline assessments for each patient and maximum of post-baseline assessments for each patient will be presented by dose cohort and overall, where geometric mean is

$$\mu_{\mathbf{g}} = \sqrt[n]{A_1 A_2 \cdots A_n}.$$

and geometric SD is

$$\sigma_g = \exp \sqrt{rac{\sum_{i=1}^n (\ln rac{A_i}{\mu_g})^2}{n}}.$$

The Wilcoxon singed-rank test will be performed to see the difference between the baseline assessments and the mean of post-baseline assessments for each cohort and overall as well as the difference between the baseline assessments and the maximum of post-baseline assessments for each cohort and overall. Bar plot of mean and SE of baseline and mean of post-baseline assessments will be presented as well as baseline vs. maximum of post-baseline assessments stratified by both dose cohorts and cancer types. Similar bar plots are generated for the median and quartiles.

The percent change from baseline will be presented over time graphically. A by-patient listing will be provided.

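### The signed-rank test of baseline CTL against each patient's maximum post-baseline CTL is not valid for patients with two or more post-baseline draws

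*SAP*

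**What the plan says.** SAP Section 8.6.3.1 plans two Wilcoxon signed-rank comparisons for CTL. One is of "the difference between the baseline assessments and the mean of post-baseline assessments for each cohort and overall"; the other is of "the difference between the baseline assessments and the maximum of post-baseline assessments for each cohort and overall". Bar plots of the same quantities follow, including "baseline vs. maximum of post-baseline assessments stratified by both dose cohorts and cancer types".

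SAP Section 8 fixes the baseline: "Baseline will generally be defined as data obtained as the last non-missing value prior to the first dose of study drug". That is a single value, although CTL is drawn both at screening and before dosing on Day 1. SAP Section 8.3 admits to the CTL population any patient with a baseline value of "percentages of WT1-positive cells among CD8-positive cells and at least one post-baseline assessment", so the number of post-baseline draws can be as low as one.

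The schedules (SAP Section 6.1, Tables 1 to 4) set many draws per patient. No alpha, permutation reference, matched number of baseline draws, fixed visit or caveat is given for the test of the maximum.

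**The concern.** One baseline value is compared with the best of several later values. Ordinary visit-to-visit variation makes the best of several exceed a single value more often than not, even when nothing has changed. The signed-rank test assumes that the differences are symmetric about zero under no effect. That assumption fails for every patient with two or more post-baseline draws.

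The study has no control arm to show what the maximum does without vaccine, so a small p-value could be read as an immune response. The groups most exposed are the large ones. The overall test draws on the full study ("Approximately 60 to 80 patients total in Parts 1 and 2 including replacements will be dosed in this clinical trial"). A dose cohort is defined by starting dose, so the RP2D level may hold 30 or more patients ("Enrollment of up to 3 RP2D cohorts of 10 patients each of a specific tumor type may take place at this dose").

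**Working it through.** The SAP states no alpha, power or sample size for this test, so there is no planned figure to reproduce.

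**Inputs from the documents**
- Part 1 post-baseline CTL draws: Days 8, 15, 22, 29, 43, 57, 71, 85 = 8 by Day 85 (Tables 1 and 2), plus maintenance doses and End of Study.
- Part 2: Days 8, 15, 22, 29, 36, 43, 50, 57 = 8 by Day 57 (Table 3), plus later phases and End of Study.
- Overall size: 60 to 80 dosed; 70 is used here. The CTL population may be smaller.

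**Assumptions not in the documents:** two-sided 0.05; lognormal values with within-patient log SD 0.3 to 0.6 and serial correlation 0 or 0.6; the mix of draw counts; the share of patients whose values are always 0. Zero differences are dropped.

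**Step 1, exact.** If baseline and k later values are exchangeable and continuous, each of the k+1 is equally likely to be the largest. So P(maximum > baseline) = k/(k+1):

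| k | 1 | 2 | 4 | 8 |
|---|---|---|---|---|
| P | 0.50 | 0.667 | 0.80 | 0.889 |

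Only k = 1 satisfies the null.

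**Step 2, hand check at 70 patients.** Count the positive differences and use z = (70P − 35)/(√70/2), with √70/2 = 4.18. This is a sign test, so only a guide to the signed-rank result.
- Eight draws each: 70 × 0.889 = 62.2; z = 27.2/4.18 = 6.5.
- k mixed equally over 1, 2, 4, 8: P = (0.5 + 0.667 + 0.8 + 0.889)/4 = 0.714; 70 × 0.714 = 50.0; z = 15.0/4.18 = 3.6.
- k mixed over 1, 1, 2, 4: P = (0.5 + 0.5 + 0.667 + 0.8)/4 = 0.617; 70 × 0.617 = 43.2; z = 8.2/4.18 = 1.95, which is almost at the 1.96 threshold, so rejection is near even odds.

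If half the patients are always 0, 35 differences remain and √35/2 = 2.96. The two mixed cases then give z = (25.0 − 17.5)/2.96 = 2.5 and (21.6 − 17.5)/2.96 = 1.4.

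**Step 3, simulated rejection by the signed-rank test with no effect, n = 70**

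| Draws per patient | No zeros | Half the patients always 0 |
|---|---|---|
| 1 | about 5% | not needed: null holds |
| 8 | about 100% | over 99% |
| 1, 2, 4, 8 equally | about 94-98% | about 70-80% |
| 1, 1, 2, 4 | about 47-55% | about 27-29% |

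**Step 4, cohorts.** The smallest two-sided exact p is 2 × 0.5^n: 0.0625 at n = 5 and 0.031 at n = 6. Cohorts of 5 or fewer cannot reach 0.05. With eight draws and no zeros, rejection is 39-49% at n = 6, 74-81% at n = 10 and over 99% at n = 30. At n = 6 it falls to 4-6% if 30% of patients are always 0.

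**Step 5, the companion test of the mean.** On the raw scale, the mean of several skewed values tends to lie above a single skewed value. With eight independent draws at n = 70, rejection with no effect is about 10-25% at log SD 0.3 to 0.6 and about 44-57% at 0.9 to 1.2. On the log scale it is about 5% (no zeros).

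**The case against.** The best defence is about scope. The test sits under exploratory analyses, with no alpha, no decision rule and no link to dose selection. The secondary variable in SAP Section 6.3 is CTL at each assessment time, not the maximum. Section 8.6.3 also plans a "Spearman rank correlation and 95% CI between the level of expression of WT1 protein and the degree of the immune response", which does not rest on selecting the largest value when done visit by visit. All of this stands and limits the severity. It does not make the test valid: exploratory status excuses a lack of multiplicity control, not a null that is false by construction.

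A reader might infer that the overall test is bound to be significant. The documents do not support that. They give neither the dropout pattern nor the share of zeros. The SAP expects some baselines of 0 and has a responder rule for patients with four or fewer post-baseline visits. With few draws or many zeros, rejection is well above 5% but can be below one half.

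A reader might also infer that the cohort tests are all inflated. Those with 5 or fewer patients cannot reach 0.05, the result at 6 depends heavily on zeros, and the RP2D expansion is optional.

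Nor do the bar plots become misleading between Parts 1 and 2. At matched follow-up to Day 85 (8 against 10 draws), the no-effect median ratio of maximum to baseline is 1.53 against 1.58 at log SD 0.3, and 2.34 against 2.51 at 0.6. That gap is too small to pursue.

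**Conclusion.** The point holds. The invalidity for two or more draws is exact, given exchangeable continuous values under no effect, and nothing in the SAP corrects it. Its size depends on assumptions about alpha, draw counts and zeros. At about 70 patients the false-positive rate runs from about 27% in the sparsest case examined to about 100% with eight draws each, against a nominal 5%. A significant overall result with no effect is to be expected only if most patients have several non-zero draws, which is what the schedule intends for those who stay on treatment.

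This should be fixed, but it is confined to one exploratory p-value. Conclusions on DLT, MTD and safety do not depend on it.

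**What to change.** 1. Delete the signed-rank p-value for the maximum in SAP Section 8.6.3.1. Keep the maximum as a descriptive summary, and show the number of post-baseline draws per patient beside it.
2. Do not let the raw-scale mean test become the inferential one unchanged, given its own inflation with skewed data. Replace it with one of these:
   - a signed-rank test of log baseline against the mean of the log-transformed post-baseline values, with a stated rule for zeros. The geometric means planned in the same section need such a rule in any case;
   - a signed-rank test of baseline against one pre-specified visit, such as Day 29. This is the k = 1 case, with simulated rejection of 4.3-6.5% at 60 to 80 patients. It leaves out patients without that visit.

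Cost: one exploratory p-value is lost, with a change of SAP wording and minor programming. No new samples or patients are needed.

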## 8.6.3.2. Immune Response

Peripheral blood samples will be obtained for evaluation of WT1 peptide-specific CTL induction activity by tetramer assay and WT1 serum antibody titer by enzyme-linked immunosorbent assay (ELISA), and for isolation of PBMCs. In addition, blood samples will be obtained and blood serum archived for possible analyses of other biomarkers, such as protein and microRNA, that may be important to the understanding of WT2725 but which have not yet been selected. These results may be presented in figures and/or patient data listings.

For DTH assessments, the number of patients who have an injection with WT2725 and control will be displayed before and after injection for each dose. The number and percentage for the reaction of positive and negative based on the number of patients who have injections may also be presented for the WT2725 versus negative control. The summary for all the dose will also be generated. The patients who have at least one injection will be present. The number of positive reaction for overall is counted for the patients who have at least one positive reaction during all the doses. The number of negative reaction for overall is counted for those patients who have all negative reaction during all the doses. The corresponding percentage will also be displayed similary for each dose. The results may also be presented in data listings.

For WT1 by RT-PCR tumor marker, the descriptive statistics have been provided for the baseline, at each post-baseline assessment and change from baseline by dose cohort, including the minimum and maximum of all the post-baseline assessments.

Immunohistochemistry in tumor tissue may be evaluated by expression of CD8+, Foxp3, HLA class I, and other measurements using tumor tissue samples obtained before the first dose. Due to the sparsity of the post-baseline data, post-baseline results will only be listed but not summarized. Continuous results will be summarized in a table with mean, standard deviation, median, quartiles, minimum, and maximum. Categorical variables will be summarized in a table with frequencies and percentages. Additionally, histograms of continuous results and bar plots of categorical results will be presented.

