5. AMENDMENT NO. 3, PROTOCOL VERSION 4.0 (27 MAR 2013)

The following changes were made to the protocol:

- In order to more completely assess disease progression and patient survival, these parameters will continue to be assessed every 3 months following the end of study visit.
- As patients with Grade 2 hematology values may be enrolled in the study and hematologic toxicity has not been observed with WT2725 during this study, the dose-limiting toxicity definition related to hematology parameters has been revised to include at least a 2 grade shift.
- It is not currently known whether administering and evaluating a DTH skin test immediately associated with vaccination or remote from vaccination correlates best with other outcomes. In order to assess and compare both methods, additional DTH skin tests were added at Days 1, 29, and 85, which resulted in adding visits at Days 31 and 87 to evaluate the DTH skin tests. In order to limit the visit schedule burden on patients, Day 2 assessments were moved to Day 3 to coincide with DTH skin test evaluation from Day 1.
- In order to increase the precision of the baseline CTL value upon which changes at subsequent time points are determined, an additional baseline CTL blood sample was included during screening.
- Results of an additional historical tumor assessment prior to baseline, if available, are requested in order to provide more information on tumor progression rate.

- In order to limit testing to patients with a reasonable possibility of a positive result, clarification was provided regarding when hepatitis B and C, human immunodeficiency virus (HIV) 1, and HIV 2 testing are required at screening.
- In order to be consistent with tumor marker response criteria, the window for collection of tumor markers during screening was shortened to 14 days prior to first dose.
- As hematologic toxicity with WT2725 has not been demonstrated in this study, the inclusion criteria for bone marrow and immune reserve was revised by lowering required absolute neutrophil count from $\geq 1500/\mu\text{l}$ to $\geq 1000/\mu\text{l}$, platelets from $\geq 10.0 \times 10^4/\mu\text{l}$ to $\geq 5.0 \times 10^4/\mu\text{l}$ after stem cell transplant, and absolute lymphocyte count (ALC) from $\geq 1000/\mu\text{l}$ to $\geq 500/\mu\text{l}$ after stem cell transplant in order to allow enrollment of a greater and more relevant patient population.

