IHC tumor samples		$X^{p,q}$									
Tumor assessment	X r									X s	
Adverse events		•	•	•	•	•	•	•	•	•	-
Concomitant medications											-

Abbreviations: AML = acute myeloid leukemia, CA-125 = cancer antigen 125, CTL = cytotoxic T lymphocyte induction activity, DTH = delayed-type hypersensitivity reactivity, ECG = electrocardiogram, ECOG = Eastern Cooperative Oncology Group, FSH = follicle-stimulating hormone, HLA = human leukocyte antigen, IHC = immunohistochemistry.

irRC = immune-related response criteria, IWG = International Working Group response criteria in acute myeloid leukemia, MRI = magnetic resonance imaging,
PBMC = peripheral blood mononuclear cell, PET = positron-emission tomography, RT-PCR = reverse transcriptase-polymerase chain reaction, SPECT = single-photon emission computed tomography, WT1 = Wilms' tumor gene product 1

- a Additional dosing windows are provided for patients who may need to recover from intercurrent medical conditions (see Section 8.3.2.1 of protocol).
- b All patients should complete an End of Study visit (see Table 2) within 28 days after the last dose of study drug and prior to the start of alternate antineoplastic therapy.
- c Prior to study drug administration.
- d Includes systolic and diastolic blood pressures, pulse, respirations rate, and oral body temperature.
- e If HLA typing has been performed previously, these results may be used, otherwise HLA typing should be the first procedure performed during screening.
- f For females of child-bearing potential.
- g Includes hepatitis B and C, human immunodeficiency virus (HIV)-1, and HIV-2, if there are signs or symptoms suggestive of infection.
- h See Appendix IV of protocol for list of required laboratory tests at each visit.
- Assessment may be omitted if an assessment was performed within the previous 3 days. If there are multiple assessments the most recent ones should be used.
- j Perform DTH skin test injections approximately 48 hours (but no sooner than 24 hours) prior to the evaluation.
- k Perform DTH skin test injections immediately before administration of study drug.
- 1 If the DTH reactivity results in erythema with induration greater than 2 cm, or leads to ulceration of the skin test site, further DTH testing should not be conducted for the patient.

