<sup>d Includes systolic and diastolic blood pressures, pulse, respirations rate, and oral body temperature.

e If HLA typing has been performed previously, these results may be used, otherwise HLA typing should be the first procedure performed during screening.

<sup>f For females of child-bearing potential.

g Includes hepatitis B and C, human immunodeficiency virus (HIV)-1, and HIV-2, if there are signs or symptoms suggestive of infection.

<sup>h See Appendix IV of protocol for list of required laboratory tests at each visit.

Assessment may be omitted if an assessment was performed within the previous 3 days. If there are multiple assessments the most recent ones should be used.

<sup>1 Perform DTH skin test injections approximately 48 hours (but no sooner than 24 hours) prior to the evaluation.

- k Perform DTH skin test injections immediately before administration of study drug.
- 1 If the DTH reactivity results in erythema with induration greater than 2 cm, or leads to ulceration of the skin test site, further DTH testing should not be conducted for the patient.
- m Evaluation should be made on the planned dosing day, prior to study drug administration.
- n Evaluation should be approximately 48 hours (but no sooner than 24 hours) after the DTH skin test injection.
- o Samples obtained 6 hours (± 30 minutes) and 48 hours (± 6 hours) postdose.
- p In place of tumor tissue samples from a biopsy during screening, archived tumor tissue samples may be provided. Availability of tumor tissue samples should be determined during screening through provision of the accession number or other identification number. If necessary, the tumor tissue sample biopsy should be performed after study eligibility has been confirmed and before the first dose of study drug. The tumor tissue samples will only be provided to the sponsor for subjects who receive study drug. In place of archival tumor tissue samples, subjects with AML should have available a bone marrow aspirate and/or bone marrow biopsy with PCR for WT1 transcript performed before the first dose of study drug. Patients with AML should also have peripheral blood assessed for blasts and WT1 transcript.
- q IHC need not be performed for patients with AML provided RT-PCR for WT1 transcript is assessed.

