# 7.3. Handling of Dropouts or Missing Data

Missing observations will generally be treated as missing at random and will not be imputed, unless otherwise noted.

Adverse event and concomitant medication dates will be imputed as follows:

Start Date: If only 'day' is missing, and the month and year are not the same as the month and year of first dose, then impute day with '01'. Otherwise, if the month and year are the same as first dose date, use first dose date. If 'day' and 'month' are missing, and 'year' is not missing, then impute month and day with month and day of first dose date (assuming same 'year'). If the year is not the same as the year of first dose, impute 01 for day and 01 for month. If the start date is completely missing, it will be set to the first dose date.

Stop Date: If only 'day' is missing, impute day with last day of the month. If 'day' and 'month' are missing, and 'year' is not missing, then impute month with '12' and day with '31' (or date of study discontinuation/completion if earlier than 12-31). If the stop date is completely missing, it will be set to the date of study discontinuation/completion. A stop date will not be applied to ongoing AEs.

Note, for all listings the actual value for date (not imputed) will be presented in all data listings and imputed dates will only be used for programming flags, etc.

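### Later by-occasion DTH positivity is biased downward, because a strong reaction ends testing and the percentages use only patients injected

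*SAP*

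**What the plan says.** SAP Section 6.3 names DTH reactivity, by assessment time, as a secondary variable. Tables 1 and 2 (Part 1) and Tables 3 and 4 (Part 2) in Section 6.1 place test injections on Days -2, 1, 27, 29, 83 and 85, and 48 hours before the End of Study visit.

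A footnote to the evaluation row of Tables 1 and 3 sets the stopping rule: "If the DTH reactivity results in erythema with induration greater than 2 cm, or leads to ulceration of the skin test site", then "further DTH testing should not be conducted for the patient". No restart is described.

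Section 8.6.3.2 describes the by-dose summary as "The number and percentage for the reaction of positive and negative based on the number of patients who have injections". That sentence makes the percentages optional and contrasts WT2725 with the negative control. Further on the display is no longer optional: "The corresponding percentage will also be displayed similary for each dose". For the summary over all doses, "The patients who have at least one injection will be present", and "The number of positive reaction for overall is counted for the patients who have at least one positive reaction during all the doses".

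Section 7.3 adds: "Missing observations will generally be treated as missing at random and will not be imputed, unless otherwise noted". It makes no exception for DTH.

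The Protocol's summary of Amendment No. 3 gives the reason for the extra tests: "In order to assess and compare both methods, additional DTH skin tests were added at Days 1, 29, and 85".

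**The concern.** The event that removes a patient from later tests is a strong value of the outcome being summarised. A percentage taken over patients injected on a later occasion describes only those who have not yet reacted strongly, but the table will be read as the positivity rate of the cohort at that time. The better the vaccine works in a few patients, the lower the later percentage becomes. A reader could then take the removal of the best responders for waning immunity, or miss a true rise. Nothing planned in Section 8.6.3.2 would reveal the cause. The number injected is shown for each dose, but not how many patients went untested because of an earlier reaction.

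**Working it through.** **Stated figure.** The documents give no DTH positivity rate, no share of strong reactors and no sample size reasoning for DTH, so there is no figure to reproduce. All rates below are assumptions.

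**Reading of 'each dose'.** I take it as dosing occasion: the tests around doses 1, 5 and 9 in Part 1, and doses 1, 5 and 11 in Part 2. Section 8.6.3.2 supports this, since it displays results before and after the injection at each dose and then sums over all doses. So does the by-time definition in Section 6.3. The SAP does not say so outright.

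**Formula.** Let n patients be tested and P be positive. Let k of those positives be stopped under the rule, with no other change in status and no other loss. A stopping reaction at the WT2725 site is assumed to be read as positive.

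- Later percentage under the SAP: (P − k)/(n − k)
- Later percentage with stopped reactors kept as positive: P/n
- In proportions, with p = P/n and s = k/n, the bias is (p − s)/(1 − s) − p = −s(1 − p)/(1 − s)

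This is negative for every s > 0 and p < 1, so the direction does not depend on the assumed rates.

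**Size over an assumed range** (later percentage under the SAP, with bias in points):

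| True rate p | s = 5% | s = 10% | s = 20% |
|---|---|---|---|
| 20% | 15.8% (−4.2) | 11.1% (−8.9) | 0.0% (−20.0) |
| 40% | 36.8% (−3.2) | 33.3% (−6.7) | 25.0% (−15.0) |
| 60% | 57.9% (−2.1) | 55.6% (−4.4) | 50.0% (−10.0) |

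**In counts.** Section 4.1 plans about 10 patients at each Part 2 dose level. Take n = 10 with 4 positive and no true change.

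- One patient stopped: 3/9 = 33.3%
- Two stopped: 2/8 = 25.0%
- Stopped reactors kept as positive: 4/10 = 40.0% in both cases

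If the true count rises from 4/10 to 5/10 and two reactors have been stopped, the SAP shows (5 − 2)/(10 − 2) = 3/8 = 37.5%. A true rise from 40% to 50% then appears as a fall.

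**Overall summary.** Its denominator is anyone injected at least once, and its numerator is anyone ever positive. A stopped reactor stays in both, so the bias is zero. One caution applies. Section 8.6.3 limits its other exploratory analyses to patients measured at baseline and at least once after treatment. If that were applied to DTH, a patient stopped on a pre-dose test would leave this summary too. I follow the more specific wording of Section 8.6.3.2.

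**The case against.** The plan has a real defence. The ever-positive summary already keeps every stopped reactor, and the number injected on each occasion is displayed. DTH is listed as secondary but analysed descriptively under the exploratory heading. Section 8.6.3.2 plans no DTH test or confidence interval, and DTH does not enter the DLT or MTD decisions. The percentages are optional in one sentence and firm in another. All this limits the consequence, but it does not remove the bias from a by-occasion table that the SAP says will be displayed.

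Some stronger conclusions that a reader might draw are not supported:

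- **That a planned comparison of the remote and vaccination-associated tests is biased.** That aim appears in the Amendment No. 3 rationale, but Section 8.6.3.2 contrasts only WT2725 with the negative control. Nor is it certain that a strong remote reaction always blocks its paired test. The footnotes put both the reading and the new injection before dosing without ordering the two. The stopping footnote is also not repeated under Tables 2 and 4, which hold Days 83 to 87. Its general wording reaches those days only by inference.
- **That every stopped patient should count as positive from then on.** Tests on Days -2 and 1 are injected before any study drug, so reactivity present before vaccination would be carried forward as vaccine response. The footnote also does not say that the reaction must be at the WT2725 site.
- **That the missing-at-random statement is simply false.** Missingness that depends on an earlier recorded reaction can be missing at random. The difficulty is that an unadjusted injected-only percentage needs missingness unrelated to reactivity.
- **That the distortion is known to be very large.** Stopping 4 of 10 patients, with 1 of the remaining 6 positive, would give 1/6 = 17% against 5/10 = 50%. Nothing in the documents points to so high a stopping rate.

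**Conclusion.** The point stands for the by-occasion DTH percentages and only there. The direction is certain once any patient is stopped for a positive reaction while some others remain negative, all else unchanged. The size is unknown: about −3 to −15 points at an assumed true rate of 40% with 5% to 20% stopped, and −2 to −20 points over the wider grid. These figures rest on reading 'each dose' as dosing occasion, on stopped patients being positive and remaining so, and on no other losses. No primary conclusion is touched. The change is worth making because a listed secondary variable would otherwise be displayed with an unmarked downward bias.

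**What to change.** In SAP Section 8.6.3.2:

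1. Define 'each dose' as the DTH testing occasion, and settle whether the percentages may or will be shown.
2. At each occasion, report the number of on-study patients not tested because of an earlier reaction under the stopping rule.
3. Beside the injected-only percentage, give one that keeps in the denominator, and counts as positive, patients stopped for a positive WT2725-site reaction on a test given after the first dose.
4. Show separately the patients stopped on the Day -2 or Day 1 test, or for a control-site reaction. Do not count them as post-vaccine positives.
5. State that the injected-only percentages are conditional on no earlier strong reaction.
6. Make the ever-positive summary the main DTH summary, and say whether the Day -2 and Day 1 tests count in it.
7. If the two test methods are compared, use patients who had both tests, and give the number whose second test was withheld because of the first.

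The cost is SAP wording and a row or column in one table. No visit, and no part of the clinical stopping rule, changes. There are two disclosed weaknesses. The added percentage assumes that a strong reactor stays reactive, which is why the injected-only figure remains beside it. It also needs the stopping reason and the reaction site to be derivable from the recorded DTH data. The documents do not confirm this, so it should be checked against the CRF first.
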